### **6.3 Pharmacokinetic Population**

The pharmacokinetic (PK) population will include all participants who completed the Day 9 12-hour cocaine PK sample. The PK concentration dataset will include all participants who have at least 1 quantifiable concentration of SXC-2023, cocaine, or cocaine metabolite, benzoylecgonine (BE). The PK analysis dataset will include all participants who have sufficient concentration-time data for a given analyte to calculate PK parameters.

### **6.4 Evaluable for Subjective Effects Analysis Population**

The Evaluable analysis set will include all participants who completed all 5 infusion sessions.

## **7. STATISTICAL ANALYSES**

Descriptive statistics will be used to present study data. For continuous data, mean, standard deviation, median, 25th and 75th percentiles, minimum, and maximum will be presented. Categorical variables will be presented as counts and percentages. All data will be presented separately by treatment group. All data will be presented in listings, except for the assessments done to determine eligibility.

All the analyses of safety data for this study will be performed using SAS® statistical software package, version 9.4 or later. Additional software, such as R (version 4.5.1, The R foundation for Statistical Computing), may also be used for input data and TLFs generation if necessary.

Missing data will not be imputed for any analysis, except for partial dates for determining treatment emergent AEs and prior and concomitant medication (see [Section 7.1](#)). The numbers of data points reflected in summary statistics will be indicated by presenting the number of observations.

The pharmacokinetics data will be analyzed using Phoenix WinNonlin (Version 8.6 or later, Certara). Additional software such as R (version 4.3.3 or later, The R foundation for Computing) may also be used for input data and Tables, Listings, and Figures (TLFs) generation if necessary.

### **7.1 Handling of Partial Dates**

It is common to allow the entry of partial dates for adverse events and concomitant medications. For dates where incomplete month and/or day values are allowed, the partial dates will be imputed as follows:

For adverse event and concomitant medications start dates:

- If the month and year are provided, the day is missing, and the month and year is the same as the month and year of the first dose/infusion of any study drug, then the day of the date of the first dose/infusion will be used for the missing day.
- If the month and year are provided, the day is missing, and the month and year is different from the month and year of the first dose/infusion of any study drug, then the 1st of the month will be used for the missing day.
- If the year is provided, the day and month are missing, and the year is the same as the year of the first dose/infusion of any study drug, then the day and month of the date of the first dose/infusion will be used for the missing day and month.
- If the year is provided, the day and month are missing, and the year is different from the year of the first dose/infusion of any study drug, then the 1st of January will be used for the missing day and month.
- If the day and year is provided, the month is missing, and the year is the same as the year of the first dose/infusion of any study drug, then the month of the date of the first dose/infusion will be used for the missing month.
- If a start date is missing all date parts then first date of dose/infusion will be used.

For adverse event and concomitant medications end dates:

- If the month and year are provided, the day is missing, and the month and year is the same as the month and year of the first dose/infusion of any study drug, then the day of the date of the first dose/infusion will be used for the missing day.
- If the month and year are provided, the day is missing, and the month and year is different from the month and year of the last dose/infusion of any study drug, then the last day of the month will be used for missing day.
- If the year is provided, the day and month are missing, and the year is the same as the year of the first dose/infusion of any study drug, then the day and month of the date of the first dose/infusion will be used for the missing day and month.
- If the year is provided, the day and month are missing, and the year is different from the year of the first dose/infusion of any study drug, then the 31st of December will be used for missing day and month.
- If the day and year is provided, the month is missing, and the year is the same as the year of the first dose/infusion of any study drug, then the month of the date of the last dose will be used for the missing month.
- If end date is missing and ongoing is not missing then the adverse event or medication will be assumed to be ongoing and the end date will remain missing.
- If the imputation rules for an end date makes the end date less than the start date for an adverse event or medication, then the start date will be used for the end date.

The imputed dates will be used to determine treatment emergent adverse events and prior and concomitant medications. In their respective listings, imputed dates will be flagged. The value for the derived variable of duration for adverse events or medication will be missing if either start or end date are imputed.

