## 10 ASSESSMENT METHODS

### 10.1 Adverse Events

Reports of AEs will be elicited by a verbal probe (*e.g.*, “How are you feeling?”) administered starting with the first cocaine screening infusion on Day -2. Any events spontaneously reported by the participant or observed by the investigative staff will also be recorded. AEs will be assessed for severity and relationship to the study drug in accordance with the criteria in [APPENDIX B](#).

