## 11.6 Adverse Events Reporting

In accordance with FDA reporting requirements, all AEs occurring during the course of the clinical trial will be collected, documented, and reported by the Investigator or sub-Investigators according to the specific instructions detailed in this section of the protocol and in [APPENDIX B](#). The occurrence of AEs will be assessed starting when the participant receives the first dose of study drug, then daily during the inpatient portion of the study until clinic release, and at the final follow-up telephone contact.

An AE is defined as any reaction, side effect, or untoward event that occurs during the course of the clinical trial, whether or not the event is considered related to the investigational product or clinically significant. For this study, events reported by the participant, as well as clinically significant abnormal findings on physical examination, vital signs, ECG, or laboratory evaluation will be recorded on the AE CRF. A new illness, symptom, sign or clinically significant clinical laboratory abnormality or worsening of a pre-existing condition or abnormality is considered an AE. Stable chronic conditions, such as arthritis, which are present prior to clinical trial entry and do not worsen are not considered AEs.

All AEs, recorded during the inpatient portion of the study regardless of severity, will be followed by study Investigator until satisfactory resolution. AEs must be reported up to the date of final follow-up following hospital discharge. At the follow-up phone call, AEs will be recorded and followed; they will be followed to resolution only if they are serious, or if the study Investigator assesses them to be clinically significant.

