## **7.4 Primary Outcome Measures**

### **7.4.1 Adverse Events**

AE data will be compiled for the SXC-2023 and placebo groups and presented as summary statistics for the safety population. A new illness, symptom, sign or clinically significant clinical laboratory abnormality or worsening of a pre-existing condition or abnormality is considered an AE. AEs will be coded using the most recent version of the Medical Dictionary for Regulatory Activities (MedDRA) preferred terms and will be grouped by system, organ, class (SOC) designation. Listings of each individual AE including start date, stop date, severity, relationship, outcome, and duration will be provided.

The number (and percentage) of participants with treatment emergent adverse events (events started after the first dose of study medication or events present prior to start of double-blind treatment but increased in severity based on preferred term) will be summarized in the following ways:

- by treatment, primary system organ class and preferred term.

- by treatment, primary system organ class, preferred term, and maximum severity.

Separate summaries will be provided for related (definitely, probably, or possibly) adverse events for treatment emergent adverse events and serious adverse events (separately for SXC-2023 and cocaine). Listings of all adverse events and serious adverse events will be provided. Additionally, a listing will be provided for adverse events leading to death, withdrawal or discontinuation.

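### The SAP's adverse event tables do not isolate the SXC-2023-plus-cocaine sessions, the treatment-emergent definition has two possible starting points, and the end-date imputation rules fail as written

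*SAP*

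**What the plan says.** SAP 7.1 completes partial dates for adverse events and medications. For a start date with the day missing, where "the month and year is the same as the month and year of the first dose/infusion of any study drug", the rule is that "the day of the date of the first dose/infusion will be used for the missing day"; in any other month the 1st is used. A start date with only the year known follows the same pattern. For a fully undated start: "If a start date is missing all date parts then first date of dose/infusion will be used".

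The end-date list repeats the first-infusion wording for the same-month and same-year cases. Its second bullet, which assigns the last day of the month, tests the month of the last dose instead. Only the missing-month rule points to the end of dosing: "then the month of the date of the last dose will be used for the missing month". If an imputed end falls before the start, "then the start date will be used for the end date". Duration is left missing whenever a date is imputed. Imputed dates decide treatment-emergent status and whether a medication is prior or concomitant.

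SAP 7.4.1 defines treatment-emergent as "events started after the first dose of study medication or events present prior to start of double-blind treatment" that then worsened. It specifies two tables: by treatment, SOC and preferred term, and the same with maximum severity. Related events are also summarised separately for SXC-2023 and for cocaine. SAP 7.4.2, by contrast, summarises HR and BP by treatment, cocaine dose and infusion session.

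On collection, protocol 10.1 has the verbal probe "administered starting with the first cocaine screening infusion on Day -2", Table 2 marks adverse events from Day -3, and protocol 11.6 states: "The occurrence of AEs will be assessed starting when the participant receives the first dose of study drug". Appendix B also starts from the first dose of study drug.

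**The concern.** The primary objective (SAP 3.1) is interaction between SXC-2023 and 20 mg and 40 mg of cocaine given together. Only Sessions 4 and 5 (Days 8 and 9) provide that combination. Sessions 1-3 are cocaine without SXC-2023, and Days 3-7 are SXC-2023 or placebo without cocaine. A table by arm alone does not show which exposure produced an event.

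The definition adds a second problem. *Study medication* is not defined, and the worsening clause uses a different starting point, the beginning of double-blind treatment. Depending on the reading, the tables either mix in events that precede SXC-2023 or can lose events whose start date is incomplete. With about 10 participants per arm, one reclassified participant moves a rate by 1/10, or 10 percentage points.

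The end-date rules are a separate fault. Placing an unknown end at the first infusion closes an event or medication at the earliest possible point, and two of the bullets do not fit together.

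**Working it through.** **Inputs.** First infusion: Day -2, cocaine 20 mg (SAP 4.1). SXC-2023/placebo: Days 3 to 9. Combination sessions: Days 8 and 9. There is no Day 0, so Day 3 is 4 days after Day -2 and Day 9 is 10 days after it. The plan gives no figure of its own to reproduce. Assumption: Day -2 is equally likely to be any date of a 365-day year.

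**Which date is the anchor?** SAP 7.1 does not print Day -2; it is an inference. SXC-2023 is oral, so an infusion can only be cocaine or saline, and SAP 7.3 counts cocaine Sessions 1-5 under study drug exposure. Against this, the stopping rules (SAP 4.4.1) name study drug and cocaine as separate things.

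**Start dates with the Day -2 anchor.** With only the day missing, an event with true onset on Day d is placed on or after Day 3 only if the 1st of a month falls on one of Days 3 to d, which is d − 2 dates. The share placed before Day 3 is therefore 1 − 12(d − 2)/365:

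| True onset | Calculation | Placed before Day 3 |
|---|---|---|
| Day 8 | 1 − 72/365 | 80% |
| Day 9 | 1 − 84/365 | 77% |
| Day 11 | 1 − 108/365 | 70% |
| Day 18 | 1 − 192/365 | 47% |
| Day 21 | 1 − 228/365 | 38% |

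With only the year known, the share is 1 − (d − 2)/365: 1 − 6/365 = 98% for Day 8 and 1 − 7/365 = 98% for Day 9. Fully undated: 100%. With the anchor at the Day 3 dose, the share is 0% in every case.

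**What that does to the tables.**
- *Study medication* includes cocaine: misdated events stay in, and so does every event from Days -2 to 2.
- *Study medication* means SXC-2023/placebo: Days -2 to 2 are excluded unless an event worsens, and events misdated to Day -2 can drop out with them.
- Either way, neither specified table separates Days 8 and 9 from the other days counted. The second reading still pools Days 3-7, Days 8-9 and follow-up.

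**End dates, day missing.** Let the first infusion fall in month A and the last dose (Day 9) in month B.
- A and B the same: an end on Day 9 is set to Day -2, then raised to the start date if that is later. Share of calendar positions: 1 − 120/365 = 67%.
- A and B different, end in A: bullet 1 gives the first-infusion date and bullet 2 gives the last day of A. Both apply and they can disagree.
- A and B different, end in B: bullet 1 fails because B is not A, and bullet 2 fails because it requires a month other than B. No rule applies.

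A and B differ when a month start falls in the 10 days after Day -2: 12 × 10/365 = 33%.

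**The case against.** Several limits are fair.

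- **The two start-date harms cannot both occur.** A reader might infer that the tables lose undated events and are also swamped by cocaine-only ones. Those need opposite readings of *study medication*. The loss further requires SAP 7.1 to count cocaine as study drug while 7.4.1 does not; if both sections exclude cocaine, the anchor is Day 3 and nothing is lost this way.
- **Few dates should be missing.** Participants are inpatients with daily adverse event checks, and the data system queries missing entries. The percentages above are conditional on a date being incomplete. The 33% is a share of calendar positions, not of participants harmed.
- **The follow-up call is a likelier source of vague dates, but loss is not automatic.** Onset on Days 18-21 with the day missing lands before Day 3 in 47% to 38% of positions.
- **End dates do not decide treatment emergence.** The floor at the start date and the blanked duration confine the effect mainly to medication status and listings. Protocol 8.5 already bars most medications before intake.
- **The tables would not generally be at a ceiling.** A reader might infer this from the 96% (25 of 26) with euphoric mood in the earlier interaction study cited in protocol 2.2.2.2. That is one term; the next most frequent are 42% and 38%. Both arms also receive cocaine in Sessions 4 and 5, so a period split may not remove that ceiling.
- **The by-arm contrast is still informative.** Cocaine exposure is planned identically in both arms, every event is listed with its start date, and the table shells are in a separate document. A by-period table may be planned there.
- **Baseline-session events are planned to be collected.** Protocol 10.1 and Table 2 cover them. The wording in 11.6 and Appendix B needs aligning, but it does not show that the data will be missing.

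These points limit the size of the date problem. They do not repair the end-date rules, supply the missing definition, or put a period split into the plan for a primary endpoint. The related-event summaries split by the investigator's attribution, not by exposure period.

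**Conclusion.** The point holds as a matter for correction in the SAP. The most important part is that the specified adverse event tables do not isolate Days 8 and 9, although the objective concerns that combination and HR and BP are already summarised by session and cocaine dose. This does not depend on any reading of the terms; it rests on the tables named in SAP 7.4.1, since the shells are not available.

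The two-anchor definition is a real ambiguity with one of two consequences: pooling Days -2 to 2, or possible loss of incompletely dated events. The size of any loss is high per affected event (80% and 77% for Day 8 and Day 9 onsets with the day missing) but probably small in total. It assumes the Day -2 anchor and uniform calendar starts.

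The end-date rules are wrong as written. They overlap or leave a gap in about 33% of calendar positions, and otherwise set a same-month end to the first infusion. The practical effect is mainly on medication status and listings.

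**What to change.** **SAP 7.4.1.** Define treatment-emergent as onset or worsening on or after the first SXC-2023/placebo dose (Day 3), and use that single anchor for both clauses. Tabulate adverse events by arm and period: Sessions 1-3 (cocaine alone); Day 3 to before Session 4; Session 4 (20 mg); Session 5 (40 mg) to follow-up.

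**SAP 7.1.** Define *study drug*, and use *study medication* consistently with it. Impute incomplete adverse event start dates to the first SXC-2023/placebo dose when the known date parts allow it. Impute incomplete end dates to the last possible date, meaning the end of the known month or year, capped at last contact. This replaces the two clashing bullets.

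**Protocol 11.6 and Appendix B.** Align the first-dose wording with 10.1.

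**Cost.** SAP wording, a protocol clarification and a few more tables, from data already collected. Cells will be small with about 10 per arm. The Day 3 anchor protects treatment-emergent status but cannot recover the true period, and it may count a vaguely dated baseline event as treatment-emergent. The period tables should therefore footnote how many onsets were imputed; SAP 7.1 already flags these dates in the listings.

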## **7.2 Demographic and Baseline Characteristics**

### **7.2.1 Subject Disposition and Withdrawals**

The number of participants included in each population will be summarized by treatment and along with the reason for exclusion and discontinuations.

### **7.2.2 Demographics and Baseline Characteristics**

Demographics and baseline characteristics (age, gender, ethnicity, race, height, weight, and BMI) will be summarized by population, treatment group and overall.

### **7.2.3 Medical History and Physical Examination Findings**

Relevant medical histories and current medical conditions at baseline will be summarized by system organ class and preferred term, by treatment group for the safety population. Listings will also be provided.

### **7.2.4 Prior and Concomitant Medications**

Prior and concomitant medications will be coded according to the World Health Organization drug dictionary (WHO DD). A summary of concomitant medications will be provided for the safety population by Anatomic Therapeutic Class (ATC), WHO DD Level 4, and treatment. A listing of prior and concomitant medication will also be provided.

## **7.3 Exposure**

The summary of study drug exposure by dose day (Day 1-9) of SXC-2023 or placebo and by cocaine infusion session (1-5) will be summarized for the safety population of descriptive statistics (counts and percentages). A listing will also be provided.

## **7.4 Primary Outcome Measures**

### **7.4.1 Adverse Events**

AE data will be compiled for the SXC-2023 and placebo groups and presented as summary statistics for the safety population. A new illness, symptom, sign or clinically significant clinical laboratory abnormality or worsening of a pre-existing condition or abnormality is considered an AE. AEs will be coded using the most recent version of the Medical Dictionary for Regulatory Activities (MedDRA) preferred terms and will be grouped by system, organ, class (SOC) designation. Listings of each individual AE including start date, stop date, severity, relationship, outcome, and duration will be provided.

The number (and percentage) of participants with treatment emergent adverse events (events started after the first dose of study medication or events present prior to start of double-blind treatment but increased in severity based on preferred term) will be summarized in the following ways:

- by treatment, primary system organ class and preferred term.

- by treatment, primary system organ class, preferred term, and maximum severity.

Separate summaries will be provided for related (definitely, probably, or possibly) adverse events for treatment emergent adverse events and serious adverse events (separately for SXC-2023 and cocaine). Listings of all adverse events and serious adverse events will be provided. Additionally, a listing will be provided for adverse events leading to death, withdrawal or discontinuation.

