### **12.4 Safety Data Analyses**

#### **12.4.1 Adverse Events (AEs)**

AEs will be coded using the most recent version of the Medical Dictionary for Regulatory Activities (MedDRA) preferred terms and will be grouped by system, organ, class (SOC) designation. The severity, frequency, and relationship of AEs to study drug will be presented by preferred term by SOC grouping. Listings of each individual AE including start date, stop date, severity, relationship, outcome, and duration will be provided.

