### **13.3 Data Editing and Control**

Automated edit checks for missing, discrepant, and out-of-range data will be programmed into the study electronic data capture system (EDC). The identified discrepancies will be presented to the site user for resolution or justification. A TRI Data Manager will review the justification for all unresolvable discrepancies and will close or re-query them. Once all discrepancies and queries have been resolved, the PI will review the eCRFs in the EDC and confirm their accuracy with his/her electronic signature.

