### **13.5 Data Processing**

A database will be constructed from the eCRFs that captures each item of data from each eCRF. All eCRFs will undergo a single-data entry process into the main study database with 100% quality control verification of all data entered into the eCRF. After entry, the data will be validated both manually and electronically. The database will undergo 100% quality assurance audit before locking and release for statistical analysis.

All AE information will be entered into the main study database from the AE CRF. AEs will be coded using the most recent version of the Medical Dictionary for Regulatory Activities (MedDRA) preferred terms and will be grouped by system, organ, class (SOC) designation. The severity, frequency, and relationship of AEs to study drug will be presented by preferred term by SOC grouping. Listings of each individual AE including start date, stop date, severity, relationship, outcome, and duration will be provided.

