### C. DEFINITIONS – RELATEDNESS OF EVENTS

The study Investigator is responsible for defining, in his/her best judgment, the relationship of the AE/SAE to the investigational product. The degree of certainty for which the AE/SAE is attributed to the investigational product or alternative causes (*e.g.*, natural history of the underlying disease, concomitant therapies, *etc.*) should be determined by how well the experience can be understood in terms of one or more of the following:

- ***Exposure:*** Is there evidence that the participant was actually exposed to the investigational product?
- ***Timing of the administration of investigational product:*** Did the AE/SAE follow in a reasonable temporal sequence from administration of the investigational product?
- ***Consistency with investigational product safety profile:*** Known pharmacology and toxicology of the investigational product in animals and man; reaction of similar nature having been previously described with the investigational product.
- ***Alternative explanations*** for the adverse event such as concomitant medications, concurrent illness, non-medicinal therapies, diagnostic tests, procedures or other confounding findings.
- ***Response to discontinuation*** of the investigational product.

Terms and definitions to be used in assessing the investigational product relationship to the AE/SAE are:

- **Unknown:**  
Use this category only if the cause of the AE/SAE is not possible to determine.
- **Definitely Not Related:**  
The participant did not receive investigational product, the temporal sequence of the AE/SAE onset relative to administration of the investigational product is not reasonable, or there is another obvious cause of the AE/SAE.
- **Unlikely Related:**  
There is evidence of exposure to the investigational product or there is another more likely cause of the AE/SAE.
- **Possibly Related:**  
There is evidence of exposure to the investigational product, the temporal sequence of the AE/SAE onset relative to administration of the investigational product is reasonable, but the AE/SAE could have been due to another equally likely cause.
- **Probably Related:**  
There is evidence of exposure to the investigational product, the temporal sequence of the AE/SAE onset relative to administration of the investigational product is reasonable, and the AE/SAE is more likely explained by the investigational product than by any other cause.
- **Definitely Related:**  

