### **6.2 Safety Population**

The safety population will include all participants who are included in the FAS population and who received any study drug.

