## **8. TABLES, FIGURES, LISTINGS, AND APPENDICES**

The proposed listing of tables, figures, and listings to be generated with the analysis and included in clinical study report is presented in a separate document.

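### The closed list of related grades in SAP 7.4.1 leaves events graded Unknown out of the related TEAE and SAE summaries, unlike the trial's own stopping rules

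*SAP*

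**What the plan says.** Protocol Appendix B section C gives the investigator six relatedness grades: Unknown, Definitely Not Related, Unlikely, Possibly, Probably and Definitely Related. The instruction for Unknown is: "Use this category only if the cause of the AE/SAE is not possible to determine". It names both AEs and SAEs.

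SAP 7.4.1 then fixes which grades count as related: "Separate summaries will be provided for related (definitely, probably, or possibly) adverse events for treatment emergent adverse events and serious adverse events", with one set for SXC-2023 and one for cocaine. The same section plans two all-causality TEAE tables, one by system organ class and preferred term and one that adds maximum severity. It also plans listings of each individual AE that show the relationship grade.

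Protocol 12.4.1 promises a wider display: "The severity, frequency, and relationship of AEs to study drug will be presented by preferred term by SOC grouping". SAP 7.4.1 describes no table by all grades. SAP 8 refers to a list of outputs to be "included in clinical study report is presented in a separate document", which is not available for this review.

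The stopping rules (Protocol 9.10 and 9.12; SAP 4.4.1 and 4.4.2) use a different standard. An SAE counts towards stopping unless it is clearly unrelated to study drug or cocaine.

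**The concern.** AEs are a primary endpoint, and the trial asks whether two drugs interact. On Days 8 and 9 the oral dose comes about 3 hours before the first infusion, and cocaine is given at that infusion or 60 minutes later, so about 3 or 4 hours after the oral dose. Attributing an event to one drug or the other can be hard in that setting, and an investigator might reasonably use Unknown.

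The related summaries are where a reader looks for attributed harm. An event whose cause could not be determined would be absent from them, just like an event judged unlikely or definitely not related. The same event, if serious, could stop a participant, and two similar ones could halt enrolment. The plan would then apply a cautious standard to conduct and a less cautious one to reporting.

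**Working it through.** The plan gives no figure to reproduce. The check is a comparison of the two documents, followed by a short calculation of scale.

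**Step 1: the permitted grades against the SAP list.**

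| Grade (Appendix B section C) | Judgement on cause | In the related summaries (SAP 7.4.1) |
|---|---|---|
| Definitely Related | for the drug | yes |
| Probably Related | for the drug | yes |
| Possibly Related | another cause is equally likely | yes |
| Unlikely Related | against the drug | no |
| Definitely Not Related | against the drug | no |
| Unknown | none made | no |

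Six grades are permitted and three are counted, so 6 − 3 = 3 are left out. Of those three, only Unknown makes no judgement against the drug.

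**Step 2: the stopping rules.** An SAE of undeterminable cause is not clearly unrelated. It therefore counts under Protocol 9.10 and 9.12 and SAP 4.4.1 and 4.4.2, yet is absent from the related SAE summary.

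**Step 3: where the event stays visible.** It remains in both all-causality TEAE tables by arm and in the listings that show relationship. No test in the SAP uses related AEs.

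**Step 4: how many events.** The documents give no expected number. The earlier SXC-2023 data offer a rough guide:
- Pooled studies (Protocol 2.2.1.2): 33% possibly + 6% probably + 61% unlikely or unrelated = 100%.
- Six-week study (Protocol 2.2.2.2): 16 possibly + 11 probably + 36 unrelated = 63 of 63 AEs.

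No Unknown grade was reported in either. Whether those scales offered one is not stated. Zero to a few events is a reasonable expectation here.

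**Step 5: scale of one event.** SAP 6.2 sets the denominator: "The safety population will include all participants who are included in the FAS population and who received any study drug". SAP 4.2 randomises 10 per group, so about 10 per arm if nearly all are dosed. One participant whose only event for a term is graded Unknown moves that term's related rate by 1/10 = 10 percentage points. With exact (Clopper-Pearson) 95% intervals, 0/10 gives 0 to 30.8% and 1/10 gives 0.3 to 44.5%. This would be true of any single event in an arm of 10; it shows scale and does not estimate how often the problem will occur.

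**The case against.** The best defence is that the SAP does give a rule. Its list is closed, and two programmers would build the same table from it. That stands: the issue is which convention was chosen, not ambiguity.

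A reader might infer that these events would be reported as not related. The documents do not support this. SAP 7.4.1 plans no table of unrelated events, and absence from a subset defined by three named grades is literally correct. Nor are the events hidden: with about 20 participants, Unknown grades can be counted from the listings. The display promised in Protocol 12.4.1 might also show Unknown as its own category, if it is in the unseen list of outputs.

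A reader might also extend the point to grades still missing at database lock, since SAP 7 says: "Missing data will not be imputed for any analysis, except for partial dates for determining treatment emergent AEs" (prior and concomitant medication is the other use of imputed dates). That extension has almost no content. Protocol 13.3 programs edit checks for missing data, and Protocol 13.5 adds full quality control and states: "The database will undergo 100% quality assurance audit before locking and release for statistical analysis". No exception to the no-imputation rule is needed.

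Three further limits stand:
- Appendix B sends an event with an equally likely other cause to Possibly Related, which is counted. That leaves a narrow field for Unknown.
- The initial SAE report in Appendix B section E uses five grades without Unknown. This weakens the SAE half but does not remove it, because section C allows Unknown for SAEs.
- Decisions on participant safety already follow the cautious standard.

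What survives is that the related summaries, read on their own, follow a less cautious convention than the stopping rules and do not show how many events this affects.

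**Conclusion.** The point holds as a minor improvement. Followed literally, SAP 7.4.1 leaves events of undeterminable cause out of the related TEAE and related SAE summaries, while the stopping rules would count such an SAE. The effect is confined to descriptive summaries. It changes no test and loses no event from the all-causality tables or the listings.

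The conclusion rests on three assumptions:
- The relatedness scale in Appendix B, written for the investigational product, is also used for the separate cocaine summaries. The documents give no other scale for cocaine.
- The separate list of outputs does not already contain a table by all relationship grades. If it does, the count of Unknown grades is already shown and little remains to change.
- Investigators use Unknown at least once. If they never do, nothing changes.

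**What to change.** In SAP 7.4.1, state that Unknown is counted as related in the related TEAE and related SAE summaries. Footnote the number of Unknown grades per arm, separately for SXC-2023 and for cocaine, so that a reader can take them out again. A separate Unknown row in the same summaries, without reclassification, is an acceptable alternative. Settle the choice before unblinding, so that it does not depend on which arm the events fall in.

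The cost is one sentence and one footnote, with no new data. The downside is that related rates may be slightly less favourable in either arm and may include events the drug did not cause. One undeterminable event may also appear under both drugs, which blurs attribution a little; the footnote limits that, and the separate row avoids it.
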